12. Clinical laboratory tests will include: 
 a. Chemistry: sodium, potassium, chloride, calcium, phosphate, magnesium, bilirubin (total and direct), AST, ALT, GGT, ALK phosphatase, creatinine, eGFR, uric acid, BUN/Urea, glucose, amylase, lipase, total protein, and albumin 
 i. eGFR value will be calculated automatically in the EDC system, once lab results have been entered. b. Hematology: White cell count with differential (absolute values of neutrophil, lymphocyte, monocyte, eosinophil, and basophil), red cell count, hemoglobin, hematocrit, mean corpuscular volume (MCV), mean corpuscular hemoglobin (MCH), MCH Concentration (MCHC) and platelets count If a laboratory result comes back as abnormal and/or exclusionary, the laboratory test can be repeated per PI discretion and Medical Monitor approval before the participant is screen failed or discontinued from study participation.
13. Urine drug screen test results must be confirmed as negative for drugs of abuse prior to randomization. Use the drug screen kits provided by the study, testing for amphetamines, barbiturates, buprenorphine, benzodiazepines, cocaine, ecstasy, methamphetamine, methadone, marijuana, opiates, oxycodone, phencyclidine. If the subject tests positive for a substance but is able to provide a valid prescription from a medical professional, the Medical Monitor may give permission for the subject to enroll in the study. For this study medical marijuana (or equivalent) use is allowed depending on regional legality.
14. Subjects will be tested for pregnancy if they are women of childbearing potential. A serum pregnancy test will be performed if the urine pregnancy test is positive. Subjects with positive serum pregnancy test results will be discontinued from study participation.
15. At Baseline, all subjects will have a full urinalysis panel completed. After baseline, a urine dipstick analysis will initially be done to assess urine health. Microscopic examination (urinalysis) will only be performed if the dipstick test is abnormal for leukocyte, blood, nitrite or protein. If results come back as abnormal, the laboratory test can be repeated per PI discretion and Medical Monitor approval
16. Confirm whether subject has signed consent for the optional biobanking sub-study.

17. 10 ml of blood will be collected and banked at NYU biorepository for the EPPIC-Net repository (see instructions for how to collect blood samples).

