3. NIH HEAL CDE
 - a) PGIC
4. Blood Collection – Lab Chemistry
5. Urine Collection – urine dipstick
 - a) If abnormal for leukocytes, blood, nitrite, or protein, complete full urinalysis.
6. Other Assessments
 - a) Document concomitant medications (using generic names).
 - b) Review of analgesic rescue medication with the patient
 - c) ECG (12-Lead)
 - d) Record adverse events
 - e) Drug Accountability and Compliance
7. Use Almac's IXRS to get the next kit assignment.
 - a) Dispensation of study drug (1 kit; 2 bottles)

Remote procedures to be completed between V2/Week 3 & V3/Week 6:

8. Remote Protocol Patient Measures – PROs – Use NEForm App
 - a) WOMAC-A – completed once weekly
 - b) End of Day Pain Ratings – NRS (0-10) - completed once daily for the week prior to the next visit
9. Other Remote Assessments – completed once daily
 - a) Concomitant rescue medication – captures use of acetaminophen and opioids daily
 - b) Study Medication – captures time and confirms dosing twice daily
 - i. Failure to document 6 consecutive doses (3 days) of study medication is grounds for early termination. Monitor for missed doses and reeducate patient as needed.

F.1.8. Visit 3 (Week 6)

For all visits, NEForm will be used to record the PRO scales. All other data will be directly entered into the study database or collected externally and entered into the EDC with source materials uploaded to Florence. Additional information and instructions on study activities can be found in the MOP.

1. Review remote forms completion rate with patient
2. Protocol Patient Measures
 - a) PROs
 - i. WOMAC-A (Pain Scale)
Must obtain WOMAC-A before synovial fluid collection procedure
 - ii. WOMAC-C (Functional Scale).
 - iii. HADS
 - b) Staircase-Evoked Pain Assessment.
3. Lab Draws/Collections
 - a) Blood Draws:
 - i. Chemistry
 - ii. Hematology
 - iii. PK Analysis (see section F.2.2)
 - iv. Biomarker - Cytokines & Chemokines (see section F.2.2)
 - b) Urine dipstick
 - i. If abnormal for leukocytes, blood, nitrite, or protein, complete full urinalysis.
 - c) Synovial Fluid (Knee) Collection
 - i. **If subject opted out of synovial fluid DO NOT collect**
 - ii. Collect and ship to Myriad Lab for analysis
 - d) Biobanking (See Section F.2.3; See MOP, Laboratory Manual)
 - i. **If a subject has opted out of biobanking DO NOT collect**
 - ii. Collect and freeze leftover blood and synovial fluid samples to batch ship to NYU's biorepository

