7. CYP2C9 Genotyping: At the Screening Visit, a buccal swab, saliva, or blood sample will be collected to identify and exclude poor CYP2C9 metabolizers. The results must be reviewed before a subject is randomized.
8. Urine Testing:
 - At Baseline, a full urinalysis panel will be done for all subjects, including color, clarity, specific gravity, pH, leukocyte esterase, protein, glucose, ketones, bilirubin, blood, nitrite, urobilinogen.
 - After Baseline, a Urine Dipstick will be completed at all in-clinic visits and will include Calcium, Glucose, Protein, pH, Bilirubin, Blood, Urobilinogen, Micro albumin, Ascorbate, & Specific Gravity. If the dipstick test is abnormal for leukocyte, blood, nitrite or protein, a sample should be sent for a full urinalysis panel.

The required laboratory tests are listed in Table 2, below. Laboratory tests will be performed at the site, and each site will provide their laboratory certificates and normal ranges to the coordinating center. Reference ranges have been standardized across study sites for lipase and amylase due to institutional variability and are as follows, please refer to protocol *Appendix IV Amylase and Lipase Normal Ranges Memo_12Jan2024* for additional information.

F.2.1.1. Table 2: Frequency of Laboratory & Diagnostic Procedures

Laboratory Test	Frequency
Hematology (local lab) [#]	Screening and Week 6, 12, 18, and 24/ET
Chemistry (local lab) [#]	Screening, Baseline, Weeks 3, 6, 9, 12, 15, 18, 21, and 24/ET
Urine Dip Stick ^	Weeks 3, 6, 9, 12, 15, 18, 21, and 24/ET
Urinalysis (UA) ^	Complete UA panel at Baseline; for abnormalities at Weeks 3, 6, 9, 12, 15, 18, 21, and 24/ET
Pregnancy test (urine) using kit provided *	Screening, Baseline, and Weeks 12 and 24/ET
Drug Screen (urine) using kit provided	Screening and Week 24/ET
CYP2C9 Genotyping	Screening

[#] For a full list of tests conducted, please see Section F.2.1.

[^] Microscopic examination will only be performed if the dipstick test is outside of the reference range for leukocyte, blood, nitrite, or protein.

^{*} Only for WOCBP. If urine pregnancy test is positive, a serum pregnancy test will be conducted.

F.2.2. Blood and Synovial Fluid Biomarkers (Cytokines and Chemokines)

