The primary safety endpoint for the study is the following: Percent of adverse events and serious adverse events in the final 2 weeks of each treatment period. Vital signs (heart rate, blood pressure, etc.) will be obtained regularly throughout the study at the time of study visits. Height and weight will be collected during the screening period and at the subject's final study visit. Blood chemistry and hematology panels will also be obtained regularly at study visits. All ECGs will be documented by recording date, time, heart rate, QRS duration, PR interval, RR interval, QT, and QTcF on the eCRF. Paper strips will be maintained in the patient file. If indicated, additional ECG assessments can be made at the discretion of the investigator.

Because CNTX-6970 is metabolized by CYP2C9 and CYP3A4 (to a lesser extent), use of inhibitors and inducers of those two genes are excluded for the duration of participation in the trial. CYP2C9 genotyping will be used to exclude poor metabolizers. As a P-glycoprotein (P-gp) substrate, introduction of any new P-gp inhibitor is also exclusionary for the duration of study participation – P-gp use must have been chronic for at least 3 months and stable for at least 1 month prior to Baseline. Additionally, until more is known about the hepatic metabolism and renal excretion of CNTX-6970, individuals with moderate to severe impairment in hepatic or renal functioning will be excluded from participation.

ECGs will be done at each in-clinic visit to assess heart health. Urine dipstick/urinalysis and liver functioning tests (AST, ALT, GGT, total bilirubin, direct bilirubin, ALK phosphatase) will be collected at each in-clinic visit to monitor the subject's health throughout the study.

F.3. Discontinuation

F.3.1. Discontinuation of Subjects

In accordance with the Declaration of Helsinki and other applicable regulations, subjects have the right to withdraw from the study at any time, and for any reason, without prejudice to their future medical care. Subjects may be discontinued or withdrawn from the study for any of the following reasons:

- Serious adverse event.
- The investigator determines that continuation in the study would be detrimental to a subject's well-being, including criteria under F.3.1.1
- Subject fails to comply with protocol requirements.
- Subject misses more than 6 consecutive doses of study medication.
- Subject is lost to follow-up.
- Subject becomes pregnant.

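### The post-baseline dipstick list omits leukocyte esterase and nitrite, two of the four triggers for a full urinalysis

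*Protocol*

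**What the plan says.** Protocol F.2.1, item 8 describes two urine tests. At Baseline every subject has a full urinalysis panel, whose items include "leukocyte esterase, protein, glucose, ketones, bilirubin, blood, nitrite, urobilinogen". After Baseline a dipstick is done at each in-clinic visit, and its content is given as "Calcium, Glucose, Protein, pH, Bilirubin, Blood, Urobilinogen, Micro albumin, Ascorbate, & Specific Gravity".

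The dipstick decides whether a fuller test follows. The sentence after the list reads "If the dipstick test is abnormal for leukocyte, blood, nitrite or protein, a sample should be sent for a full urinalysis panel". The same four triggers appear in:

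- the footnote to Table 2: "Microscopic examination will only be performed if the dipstick test is outside of the reference range for leukocyte, blood, nitrite, or protein";
- note 15 to the Schedule of Events (Table 1): "Microscopic examination (urinalysis) will only be performed if the dipstick test is abnormal for leukocyte, blood, nitrite or protein";
- every post-baseline visit list from F.1.7 to F.1.14: "If abnormal for leukocytes, blood, nitrite, or protein, complete full urinalysis".

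F.2.7 (Safety Measures) names "Urine dipstick/urinalysis and liver functioning tests" among the tests collected at each in-clinic visit to monitor the subject's health. The SAP gives no dipstick specification.

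**The concern.** A reflex rule works only if the first test measures everything that can set it off. Here the rule names leukocyte and nitrite, and the list of what the dipstick measures contains neither. The Table 2 footnote and note 15 are restrictive: microscopic examination is done only when one of the four results is abnormal. A site that used exactly the listed strip would have no leukocyte or nitrite result to act on at any visit after Baseline. Sites whose strips differ could also apply the rule differently.

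Leukocyte esterase and nitrite are the dipstick readings that point towards urinary infection. That has some relevance for this drug. The Background cites nonclinical evidence that CCR2 plays a part in defence against microbes, and it expects a fall in peripheral monocytes. It also says the clinical relevance may be limited, and H.2.1 reports no immunotoxicity concern. What is at stake is therefore the completeness and consistency of a scheduled safety check.

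**Working it through.** The plan gives no figure to reproduce. The check compares three lists and counts how often the rule is stated.

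**Inputs**

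- Dipstick list (F.2.1, item 8): calcium, glucose, protein, pH, bilirubin, blood, urobilinogen, micro albumin, ascorbate, specific gravity. Count: 10.
- Baseline panel (same item): color, clarity, specific gravity, pH, leukocyte esterase, protein, glucose, ketones, bilirubin, blood, nitrite, urobilinogen. Count: 12.
- Triggers (same item): leukocyte, blood, nitrite, protein. Count: 4. I take the trigger called leukocyte to mean the leukocyte esterase reading, which is the term used in the Baseline panel.

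**Triggers against the two lists**

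| Trigger | Baseline panel | Post-baseline dipstick list |
|---|---|---|
| Leukocyte | yes | no |
| Blood | yes | yes |
| Nitrite | yes | no |
| Protein | yes | yes |
| Total | 4 of 4 | 2 of 4 |

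**Is the dipstick list a shortened copy of the Baseline panel?** No. The two share 7 items: glucose, protein, pH, bilirubin, blood, urobilinogen and specific gravity. The dipstick list adds 3 (calcium, micro albumin, ascorbate; 7 + 3 = 10). It leaves out 5 (color, clarity, leukocyte esterase, ketones, nitrite; 7 + 5 = 12). The three additions suggest that the list was taken from a particular strip, but the documents do not say so.

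**How often each statement appears**

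- Trigger rule: F.2.1, item 8 (1) + Table 2 footnote (1) + Table 1, note 15 (1) + visit lists F.1.7 to F.1.14 (8) = 11.
- Dipstick analyte list: F.2.1, item 8 only = 1.

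**Visits affected.** Table 2 schedules the dipstick at Weeks 3, 6, 9, 12, 15, 18, 21 and 24/ET, which is 8 visits.

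**Is a common strip specified elsewhere?** Table 2 marks the pregnancy test and the drug screen as supplied by the study (for example "Drug Screen (urine) using kit provided") and does not say this of the dipstick. F.1.2 lists a urine dipstick form for direct data entry, but its fields are not shown. Neither document contains another strip specification.

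**The case against.** The strongest reply is that this is a wording slip. The list is introduced as what the dipstick includes, and nothing says that it is complete. With the rule stated 11 times, the protocol as a whole presupposes that the strip reads leukocytes and nitrite. The strip, the data-entry form and the Manual of Procedures could each settle the point, and none is available here. That some kits are marked as supplied and the dipstick is not does not show that strips differ between sites. All of this is fair. It limits the claim to what the text specifies, and it makes an incomplete list the likelier explanation.

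A second reply is that the known renal risk is still covered. The monkey findings in A.1 were renal. Protein, micro albumin, blood and specific gravity are all on the list. Chemistry, including creatinine, eGFR and urea nitrogen, is drawn at every visit, and F.3.1.1 has a stopping criterion for creatinine. White cell counts with differential are scheduled at Weeks 6, 12, 18 and 24/ET. No endpoint, eligibility criterion or stopping criterion uses dipstick leukocyte or nitrite. This stands too, and it keeps the point well short of critical.

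Other safeguards exist but do not fill the gap. The sentence on unscheduled safety samples in item 4 of F.2.1 sits under blood tests. For urine, the opening of F.2.1 and note 15 allow repeats, but note 15 ties the repeat to an abnormal result, which an unread analyte cannot give. Adverse events are asked about at every visit, so symptomatic infection should still come to notice.

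None of this removes the mismatch. The two sentences stand next to each other, and a site following the list exactly could not carry out half of the rule.

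**Conclusion.** The concern holds. As written, 2 of the 4 dipstick results that should lead to a full urinalysis are missing from the only strip specification in the documents, at all 8 post-baseline visits. This rests on reading leukocyte as leukocyte esterase and on taking the list at face value.

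The practical effect cannot be estimated from the documents. It is zero if the strip in use reads both analytes. If it does not, reflex testing after Baseline depends on blood and protein alone. The primary efficacy analysis, power and the stopping rules are untouched. It is a modest inconsistency in a safety procedure and should be corrected.

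**What to change.** Add leukocyte esterase and nitrite to the dipstick analyte list in F.2.1, item 8. Leave the trigger wording unchanged in all 11 places. Confirm that the strip used at each site reads both analytes, and replace it with one that does where necessary. Check that the dipstick data-entry form has a field for each.

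The cost is one wording correction, a check at each site and, where needed, a different strip at visits that already take place. The downside is a few more reflex urinalyses.

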23. Female has a positive pregnancy test at the Screening or Baseline Visit, is planning to become pregnant, or is breastfeeding.
24. Has ongoing litigation for workers' compensation.
25. Known diagnosis of long QT syndrome.
26. Male has a QRS interval ≥ 120 ms *and* QTcF ≥ 460 ms OR female has a QRS interval ≥ 120 ms *and* QTcF ≥ 480 ms at Screening.
27. Has moderate to severe congestive heart failure (New York Heart Association [NYHA] class III and class IV).
28. Has a history of symptomatic cardiovascular disease.
29. Current therapy with any immunosuppressive therapy, including corticosteroids (>5 mg/day of prednisone).

30. Moderate to severe hepatic impairment at the Screening Visit, as defined by any of the following:

- AST **and** ALT values that are ≥ 1.5 times ULN

31. Moderate to severe renal impairment at the Screening Visit, as defined by either:

- An estimated glomerular filtration rate [eGFR] < 45 mL/min; or
- A serum creatinine level > 1.3 mg/dL.

32. Use of CYP3A4 inhibitors (e.g., grapefruit juice, pantoprazole) or CYP3A4 inducers (e.g., omeprazole, carbamazepine, rifampin, St. John's wort) within 7 days prior to the Baseline Visit. Please see Appendix III. Concomitant Medications.

33. Use of CYP2C9 inhibitors (e.g., amiodarone, fluconazole) or CYP2C9 inducers (e.g. carbamazepine, rifampin, St. John's wort) within 7 days prior to the Baseline Visit. Please see Appendix III. Concomitant Medications.

34. Use of P-glycoprotein inhibitors (e.g., atorvastatin, azithromycin, carvedilol) within 7 days prior to the Baseline Visit or any time during study participation, unless taken for at least 3 months prior and at a stable dose for at least 1 month prior to the Baseline Visit. Please see Appendix III. Concomitant Medications.

35. Is classified as a poor metabolizer via the CYP2C9 pathway as determined by genetic testing (CYP2C9 genotyping).

36. Has clinically significant pulmonary disease such that chronic, daily use of medical treatment is required (e.g. COPD, asthma).

37. Has any of the following blood counts:

- Monocyte count < 1 % of white blood cells (e.g., for WBC = 4,500/ μ L, exclude patient if monocyte count $< 0.01 * 4,500$ or 45/ μ L; for WBC = 11,000/ μ L, exclude patient if monocyte count $< 0.01 * 11,000$ or 110/ μ L)
- Platelet count, or
 - Females (sex at birth): $< 125,000/\mu$ L
 - Males (sex at birth): $< 150,000/\mu$ L
- Hemoglobin:
 - Females (sex at birth): < 11.5 grams/dL
 - Males (sex at birth): < 13.0 grams/dL

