Appendix III: Concomitant Medications

Subjects who take prohibited concomitant medications during the trial will be discontinued, unless the discontinuation presents an unacceptable medical risk. The justification to allow the subject to continue in the trial will be made by the Sponsor with medical input from a site investigator (PI, clinical Sub-I), and will be documented. Whether or not the participant is allowed to remain in the trial, this will be reported as a major protocol deviation and not a waiver.

The table below lists prohibitions and restrictions by medication class, including representative medications within class. Medications within each class include, but are not limited to, examples listed in this table. Any questions regarding prohibited and restricted medications should be discussed with the Medical Monitor or appropriate designee.

The direct FDA link for all CYP2C9, CYP3A4, and P-GP interactions is: [Drug Development and Drug Interactions | Table of Substrates, Inhibitors and Inducers | FDA](#)

Drug Name or Class	Episodic Use (PRN)	Chronic Use	Restrictions/Comments
Analgesics	Y	Y	
Acetaminophen, opioids, and select anticonvulsants are allowed as a rescue medication (as described in the respective sections). Other analgesics as specified below:
 
Continuous use of one of the following medications prescribed for pain is allowed: tramadol, gabapentin, duloxetine, pregabalin, milnacipran, or tricyclic antidepressants. Use must be chronic for at least 12 weeks and at a stable dose for at least 4 weeks before Screening.
 
Intermittent use of opioids is allowed if use is ongoing for at least 4 weeks before Screening, and at a frequency no more than 4 days/week, and the opioid is not taken within 24 hours of a study visit.
 
As needed use of acetaminophen is allowed.
 
Continuous use of medical marijuana (or equivalent) that is chronic for at least 12 weeks and at a stable dose for 4 weeks is allowed.
 
Continuous use of topical creams (includes CBD topicals) is allowed if use is chronic and stable for at least 12 weeks.
 
Intermittent use of topical creams is allowed if at a frequency of no more than 4 days/week.
 
Other analgesics (for example, NSAIDS) are not allowed.

Drug Name or Class	Episodic Use (PRN)	Chronic Use	Restrictions/Comments
Anesthetics, general	Y	—	If procedures requiring general anesthesia are to occur/have occurred, please contact MGH CTNI to report the medical condition(s).

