Anesthetics, local	Y	N	—
Anorexics	N	N	—
Antacids	Y	Y	—
Antiacne	Y	Y	Topical agents only, including topical antibiotics. Isotretinoin (Accutane) is not allowed.
Antiangular agents	N	N	Calcium agonists (e.g. diltiazem, nifedipine, verapamil) and beta blockers (e.g. carvedilol, propranolol, metoprolol) are excluded if used to treat angina.—
Antiarrhythmics	N	N	Amiodarone is excluded.
Antiasthma agents	Y	N	—
Antibiotics	Y	Y	Chronic use of topical antibiotics for acne is allowed, except for the MAOI linezolid (Zyvox) and isoniazid, which are not allowed. Erythromycin, clarithromycin, rifampin, and azithromycin are excluded.
Anticoagulants	N	N	Common drugs include: Warfarin (Coumadin) is not allowed. Antiplatelet agents are allowed (see “Antiplatelets”).
Anticholinergics	Y	Y	Except for scopolamine, which is not allowed.
Anticonvulsants	N	Y ^b	Gabapentin, and pregabalin are allowed. Other anticonvulsants are not allowed, including lamotrigine and carbamazepine.

Drug Name or Class	Episodic Use (PRN)	Chronic Use	Restrictions/Comments
Antidepressants	N	Y ^b	Monoamine oxidase inhibitors (which may have unknown drug-drug interactions) are excluded. Concomitant use of trazodone (up to 200mg daily), nefazodone or duloxetine are allowed. No dose changes are allowed during the study.
Antidiarrheal preparations	Y	N	Only loperamide HCl (Imodium), bismuth subsalicylate (Pepto-Bismol), and kaolin preparations are allowed.
Antifungals, systemic	N	N	
Antifungals, topical	Y	Y	
Antihistamines	Y	Y	The use of combinations containing pseudoephedrine or phenylephrine is not allowed. Combination products containing the word nighttime or are specifically marketed for before sleep routinely include an antihistamine and are not allowed. Combination products ending in “-D” routinely contain a stimulant such as phenylephrine, and the appropriate limits above apply to them. (See “Cough and Cold Preparations” for combination products.)
Antihypertensives	N	Y	Diltiazem, verapamil are excluded
Anti-impotence medications	Y	Y	—
Anti-inflammatory drugs	Y	N	Indomethacin (Indocin) and systemic corticosteroids are not allowed for PRN or chronic use. NSAID use is exclusionary.
Antimigraine	N	N	Common one includes: Triptans not allowed.

Drug Name or Class	Episodic Use (PRN)	Chronic Use	Restrictions/Comments

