Cough/cold preparations	Y	N	Use of cough and cold preparations containing pseudoephedrine or dextromethorphan is not allowed, as are those containing phenylephrine. Combination products ending in “-D” routinely contain a stimulant such as phenylephrine, and the appropriate limits apply to them. (See “Antihistamines”.)
Diuretics	Y	Y ^b	Episodic use of diuretics is restricted to treatment of premenstrual symptoms. For chronic use, medication and dosage should be stable for 1 month before screening.

Drug Name or Class	Episodic Use (PRN)	Chronic Use	Restrictions/Comments
Dopaminergics	N	Y	Common drugs include: Dopamine agonists for restless leg syndrome are allowed for chronic use.
Gastrointestinal: • H ₂ -blockers/ • proton pump inhibitors/ • prokinetic agents	Y	Y	Cimetidine (Tagamet), metoclopramide, omeprazole and pantoprazole are not allowed within 7 days of Baseline.
Hormonal (noncontraceptive) therapies	N	Y	See below.
Hormone suppressants	N	Y ^b	Only finasteride (Proscar) and dutasteride (Avodart) are allowed for chronic use. Bromocriptine (Cycloset, Parlodel) is not allowed
Hormones: reproductive	N	Y	Systemic hormonal contraceptives (oral contraceptives of estrogen and progestin combinations, depot injections such as Depo-Provera, the contraceptive implant Implanon, or transdermally delivered contraceptives such as Ortho Evra) are allowed
Hormones: thyroid	N	Y	Thyroid hormone replacement is allowed (dosage of thyroid medication should be stable for 3 months before screening).
Hypoglycemic agents	N	Y	Oral and injectable hypoglycemic agents are allowed. Insulin is not allowed
Hypolipidemics	N	Y ^b	Common drugs includes: Ezetimibe (Zetia) is allowed for chronic use.
Hypolipidemics: bile acid sequestrants	N	N	—
Hypolipidemics: fibrates	N	Y ^b	Common drugs include: Gemfibrozil and fenofibrate are allowed for chronic use.
Hypolipidemics: niacin	N	N	Common drugs include: Oral niacin and niacinamide are not allowed
Hypolipidemics: statins	N	Y ^b	Lovastatin, simvastatin, pravastatin, fluvastatin, and rosuvastatin are allowed

Drug Name or Class	Episodic Use (PRN)	Chronic Use	Restrictions/Comments
Laxatives	Y	Y ^a	Only fiber-based products and docusate sodium (Colace) are allowed
Lithium	N	Y	Stable in dosing at least four weeks prior to randomization is allowed.
Muscle relaxants	N	N	—
NMDA receptor antagonist	N	N	Common drugs include: Memantine is not allowed.

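### Appendix III does not apply the P-gp inhibitor stable-use rule consistently: it contradicts exclusion 34 for azithromycin, differs by indication for carvedilol, and leaves atorvastatin unlisted

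*Protocol*

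**What the plan says.** Three places in the protocol state one rule. Exclusion 34 (section E.4.2) bars "Use of P-glycoprotein inhibitors (e.g., atorvastatin, azithromycin, carvedilol) within 7 days prior to the Baseline Visit or any time during study participation". It lifts that bar for a drug the patient has used for 3 months or more, with no dose change in the month before Baseline. Section F.2.7 repeats the allowance ("P-gp use must have been chronic for at least 3 months and stable for at least 1 month prior to Baseline"), and section G.4 does so again in similar terms. Both F.2.7 and G.4 give the reason: CNTX-6970 is a P-gp substrate.

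Exclusion 34 then refers the reader to Appendix III. That appendix is organised by therapeutic class. It has no row for P-gp inhibitors, only a link to an FDA table, so a site has to look up each drug in its class row:

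- Antibiotics: "Erythromycin, clarithromycin, rifampin, and azithromycin are excluded".
- Antianginal agents: "beta blockers (e.g. carvedilol, propranolol, metoprolol) are excluded if used to treat angina".
- Antihypertensives: chronic use is allowed, diltiazem and verapamil are the only drugs excluded, and no duration footnote is attached.
- Statins: chronic use is allowed subject to footnote b, with the comment "Lovastatin, simvastatin, pravastatin, fluvastatin, and rosuvastatin are allowed".

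The opening of Appendix III gives the consequence: "Subjects who take prohibited concomitant medications during the trial will be discontinued". The exception is where stopping would pose an unacceptable medical risk. A major deviation is reported whether or not the patient stays in.

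**The concern.** The class rows are what a coordinator would consult when checking a medication list. If they do not carry the rule stated in exclusion 34, two sites can handle the same patient differently, one randomizing and the other screen-failing. A site can also randomize under exclusion 34 and then find at a later visit, where concomitant medications are reviewed again, that the appendix calls for discontinuation.

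Two things are at stake. First, co-medication that the protocol itself regards as relevant to drug exposure would be controlled differently from site to site. Second, a discontinuation is costly in this design. The treatment effect is estimated largely within patients over four six-week periods. Under F.3.2, a patient who stops drug without withdrawing consent is followed only to the closest of the Week 6, 12, 18 or 24 visits. Later periods are lost to the comparison.

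**Working it through.** The plan states no figure for this point, so the check sets the texts side by side. The common rule is at least 3 months of use and at least 1 month at a stable dose before Baseline. For each drug that exclusion 34 names, the question is what Appendix III says about a patient who meets that rule.

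| Drug | Exclusion 34, F.2.7, G.4 | Appendix III | Result |
|---|---|---|---|
| Azithromycin | Permitted if the rule is met | Excluded by name in the antibiotics row, no stable-use exception | Direct contradiction |
| Carvedilol | Permitted if the rule is met, no indication test | For angina: excluded however long taken. For hypertension: chronic use allowed, no duration condition in the row | Mismatch that depends on indication |
| Atorvastatin | Permitted if the rule is met | Not named. Class allowed for chronic use under footnote b | Ambiguity only |

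**Azithromycin.** The exception in exclusion 34 covers both the run-up to Baseline and continued use in the study. A long-term stable user therefore satisfies it throughout, yet Appendix III makes that patient a user of a prohibited drug. No general clause settles the matter. Section G.6 allows by default only drugs that the protocol does not specifically exclude, and azithromycin is specifically excluded.

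**Carvedilol.** The antianginal row is stricter than exclusion 34 for one indication. The antihypertensives row, read alone, is looser for another, because it lacks the footnote. The first difference has limited reach: exclusion 28 (history of symptomatic cardiovascular disease) would probably already remove most patients treated for angina.

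**Atorvastatin.** Footnote b asks for at least 3 months of use and 1 month at a stable dose, which is essentially the common rule. Its clock runs back from enrolment, whereas exclusion 34, F.2.7 and G.4 count from Baseline. The appendix says that its examples are not exhaustive, and G.6 permits what is not specifically excluded. Rows meant as closed lists, such as antidiarrheals and laxatives, say so with the word only; the statins row does not. The better reading is that a stable user is eligible under both texts, although a site could take the five named statins as the complete list.

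The tally is one contradiction, one indication-dependent mismatch and one unlisted drug.

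For scale, the SAP (section 6) assumes 15% early termination in each of four periods: 55 × 0.85⁴ = 55 × 0.522 = 28.7, the plan's figure of about 29 complete patients. Avoidable discontinuations would add to a loss that is already large. The documents give no frequency of use for any of the three drugs, so no count of such discontinuations can be computed.

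**The case against.** The strongest reply is that the criteria are cumulative. The exception in exclusion 34 lifts only exclusion 34, and because that criterion points to Appendix III, a stricter drug-specific row can apply on top of it. This answers much of the carvedilol point, since an indication-based bar is not a P-gp rule, and for hypertension exclusion 34 itself supplies the missing duration condition. It is less convincing for azithromycin. There it leaves the stable-use exception with no effect for a drug that exclusion 34 gives as an example, and neither F.2.7 nor G.4 signals any such carve-out.

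A second reply is rarity. A patient taking azithromycin for 3 months or more may well be excluded already under exclusion 16 (chronic or active infections, on the investigator's judgment) or exclusion 36 (pulmonary disease needing chronic daily treatment). That is fair, and it reduces the size of the problem.

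A third is that safeguards exist. The SAFER team confirms the other screening criteria before scheduling the interview, medication questions go to the Medical Monitor, discontinuation has a medical-risk exception, and data up to discontinuation stay in the mixed model (SAP section 7.4). These soften the consequences. However, a query to the Medical Monitor helps only if someone notices the conflict, and the major-deviation report is made even when the patient is kept.

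A reader might infer that Appendix III contradicts exclusion 34 for all three named drugs. The documents do not support that: atorvastatin is not prohibited anywhere in the appendix, and carvedilol is barred only for angina. A reader might also apply an assumed prevalence of atorvastatin use to the 55 patients and call the result the number in conflict. That would count people who, on the better reading, are eligible under both texts.

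**Conclusion.** The point holds in limited form. Appendix III directly contradicts exclusion 34, F.2.7 and G.4 for azithromycin, treats carvedilol differently according to indication, and is unclear about atorvastatin. The number of patients affected cannot be derived from the documents and is probably small. That judgment assumes that long-term azithromycin use is uncommon among otherwise eligible patients and that exclusion 28 removes most patients with angina; neither assumption can be checked here.

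The matter does not threaten the primary analysis. It is still worth correcting, because the text governs both eligibility and discontinuation for drugs that the protocol treats as relevant to exposure. As written, a patient who satisfied exclusion 34 can be reported as a major deviation. Nothing here implies a view on which status any of the drugs should have.

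**What to change.** Reconcile the antibiotics, antianginal, antihypertensives and statins rows of Appendix III with exclusion 34, F.2.7 and G.4. Give each P-gp inhibitor named in exclusion 34 one status, including any condition on indication or duration. State it in one place and have the other sections refer to it. Align the anchor date in footnote b (enrolment) with the one used elsewhere (Baseline), or say why they differ. The clinical team decides which status applies to each drug.

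The cost is a wording amendment to four table rows and a footnote, plus cross-references and notice to sites. It needs no new data, visits or patients and no change to the SAP.
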